11.1 Adverse Events

Definition of Adverse Events

Adverse Event:
	
An AE is any untoward medical occurrence in a subject or clinical investigation subject administered a pharmaceutical product, which does not necessarily have a causal relationship with this treatment.
 
An AE can therefore be any unfavorable and unintended sign (including an abnormal laboratory finding), symptom, or disease temporally associated with the use of a medicinal product, whether or not considered related to the IMP.
 
In this protocol, non-serious COPD exacerbation will not be considered as adverse events unless SAE.

TEAE for GTI 1401
	
Treatment emergent adverse events (TEAE) for GTI 1401 will defined as any adverse event occurred after or on the first study drug infusion of GTI 1401 to the final visit of GTI 1401.
 
For any subject, all AEs that occur at any time from the beginning of Alpha-1 MP administration until the final visit of the clinical trial will be considered as TEAE.
 
All tables regarding to Adverse Events are restricted to TEAE.

TEAE for GTI1401-OLE
	
Treatment emergent adverse events (TEAE) for GTI 1401-OLE will defined as any adverse event occurred after or on the first study drug infusion of GTI 1401-OLE to the final visit of GTI 1401-OLE or adverse event which continue from GTI 1401 to GTI 1401-OLE.
 
For any subject, all AEs that occur at any time from the beginning of Alpha-1 MP administration until the final visit of the clinical trial will be considered as TEAEs
 
All tables regarding to Adverse Events are restricted to TEAE.

Adverse Drug Reaction (ADR):
	
The phrase “responses to a medicinal product” means that a causal relationship between a medicinal product or study treatment and an AE is at least a reasonable possibility, that is, the relationship cannot be ruled out.

	
When an AE is classified, assessing causal relationship by the Investigator, as “definitive”, “probable”, “possible” or “doubtful/unlikely”, the event will be defined as a suspected ADR. When the causal relationship is labeled “Unrelated”, then it will be considered that the AE is not imputable to the study treatment and it is not a suspected ADR.


Serious Adverse Events (SAEs):
	
Any event reported on the AE CRF form with the serious field ticked “Yes”.
 
A SAE is any untoward medical occurrence that at any dose:
 
Results in death
 
Is life-threatening
 
Note: The term “life-threatening” in this definition refers to an event in which the subject is at risk of death at the time of the event; it does not refer to an event that hypothetically might cause death if it were more severe.
 
Requires inpatient hospitalization or prolongation of existing hospitalization
 
Results in persistent or significant disability/incapacity
 
Is a congenital anomaly/birth defect

Events of Special Interest :
	
Events of special interest include the following:
 
All COPD exacerbations occurring during the study will be recorded. Each subject will be assessed for signs and symptoms of exacerbations at each study visit as specified in Appendix 1 and Appendix 2. Given that COPD exacerbations are part of the natural history of AATD, COPD exacerbations will not be reported as AEs unless a COPD exacerbation meets the criteria of a SAE. If an exacerbation meets criteria for a SAE, it will be reported as such, and the standard of care should be followed. Results from standard of care should be obtained and reported.

Adverse events with incomplete start dates will be considered treatment emergent (TEAE) if:

- Day and Month are missing and the year is equal to or after the year of the first study drug dose date of each study (1401/1401-OLE);

- Day is missing, month is present and the month is equal or after the month of first dose of each study (1401/1401-OLE) and the year is equal or after the year of first dose date of each study (1401/1401-OLE);
- Day is missing and the year is equal to the year of the first infusion date of each study (1401/1401-OLE) and the month is equal to or after the month of the first infusion date of each study (1401/1401-OLE);
- Complete date is missing.

The AE tables will include the number and percentage of subjects by MedDRA primary System Organ Classes (SOC) - sorted by alphabetical order, MedDRA Preferred Terms (PT) - sorted by alphabetical order. A subject with more than one occurrence of the same adverse event in a particular system organ class/preferred term will be counted only once in the total of those experiencing adverse events in that particular system organ class/preferred term.

If a subject experiences the same adverse event at more than one severity, or with more than one relationship to study drug, the most severe rating or the stronger causal relationship to study drug will be given precedence. Any missing severity/relationship will be accounted as “worst case” as related in the tables.

All AE tables will be provided without separating AE occurred during treatment period with Follow-up period.

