4.6.1 Exacerbation of Chronic Obstructive Pulmonary Disease (COPD)

All COPD exacerbations occurring during the study will be recorded. The subject will be assessed for signs and symptoms of exacerbations at each study visit. Given that COPD exacerbations are part of the natural history of AATD, COPD exacerbations will not be reported as AEs unless a COPD exacerbation meets the criteria of an SAE. If an exacerbation meets criteria for an SAE, it will be reported as such, and the standard of care should be followed. Results from standard of care should be obtained and reported.

This study will use the definition of exacerbation published in the “Outcomes for COPD pharmacological trials: from lung function to biomarkers,” a report from an American Thoracic Society (ATS)/European Respiratory Society (ERS) Task Force (25). The definition of an exacerbation of COPD is an increase in respiratory symptoms (dyspnea, increased cough, and/or production of sputum) over baseline that usually requires medical intervention. Exacerbation severity is defined as:

- **Mild:** which involves an increase in one or more respiratory symptoms (dyspnea, cough, and/or sputum) that is controlled by the subject with an increase in the usual medication.
- **Moderate:** which requires treatment with systemic steroids and/or antibiotics.
- **Severe:** which describes exacerbations that require hospitalization (an emergency department stay > 24 hours is considered a hospitalization).

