5.3.2 Definition of Suspected Adverse Drug Reactions (ADRs)

All noxious and unintended responses to a medicinal product or study treatment related to any dose should be considered suspected ADRs. The phrase “responses to a medicinal product” means that a causal relationship between a medicinal product or study treatment and an AE is at least a reasonable possibility, that is, the relationship cannot be ruled out.

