5.3.3 Causal Relationship of Adverse Events

The Investigator is required to provide a causality assessment for each AE reported to the Sponsor. The Sponsor will consider the Investigator’s causality assessment. Assessment of the causal relationship to the study drug will be made according to the following classifications based on Karch FE, et al. (29):

Definite: An event that follows a reasonable temporal sequence from administration of the treatment or in which the treatment level has been established in body fluids or tissues, that follows a known response pattern to the suspected treatment, and that is confirmed by improvement on stopping the treatment (dechallenge), and reappearance of the event on repeated exposure (rechallenge).

Probable: An event that follows a reasonable temporal sequence from administration of the treatment that follows a known response pattern to the suspected treatment, that is confirmed by dechallenge, and that could not be reasonably explained by the known characteristics of the patient’s clinical state.

Possible: An event that follows a reasonable temporal sequence from administration of the treatment, that follows a known response pattern to the suspected treatment, but that could have been produced by the patient’s clinical state or other modes of therapy administered to the patient.

Doubtful/Unlikely: An event that follows a reasonable temporal sequence from administration of the treatment; that does not follow a known response pattern to the suspected treatment; but that could not be reasonably explained by the known characteristics of the patient’s clinical state.

Unrelated: Any event that does not meet the criteria above.

The operational tool to decide the AE causal relationship is based on algorithms by Karch FE *et al.* and Naranjo CA *et al.* (29,30).

When an AE is classified, assessing causal relationship by the Investigator, as “definitive”, “probable”, “possible” or “doubtful/unlikely”, the event will be defined as a suspected ADR. When the causal relationship is labeled “Unrelated”, then it will be considered that the AE is not imputable to the study treatment and it is not a suspected ADR.

In addition, when a causal relationship between the study treatment and the AE cannot be ruled out by the Investigator and/or Sponsor, it means that the AE cannot be labeled “unrelated”.

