5.3.9 Events of Special Interest

All COPD exacerbations occurring during the study will be recorded. Each subject will be assessed for signs and symptoms of exacerbations at each study visit (Section 4.6.1). Given that COPD exacerbations are part of the natural history of AATD, COPD exacerbations will not be reported as AEs unless a COPD exacerbation meets the criteria of a SAE (Section 5.3.6). If an exacerbation meets criteria for a SAE, it will be reported as such (Section 5.4.1), and the standard of care should be followed. Results from standard of care should be obtained and reported.

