11.1.1 Overview of AEs		
Population	:	Safety population
Contents	:	Overview AE table will be tabulated and will present number and percentages of subjects and number of events with following items. 
 • AEs • ADRs • AEs with fatal outcome • SAEs • AEs leading to premature discontinuation from the study • Events of special interest

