 11.1 Adverse Events
 11.1.11 Listing of Non-Serious COPD Exacerbation

Safety population

Subject Number	Start / End Date and Time of Events	Relative days*	Pattern/ Severity	Action Taken with Study Drug	Causality to Study Drug	Outcome	(a)	(b)	(c)	(d)	(e)	(f)
xxxx	yyyy-mm-ddThh:mm / vvvv-mm-ddThh:mm	x	INTERMITTENT/ MILD	DRUG WITHDRAWN	DOUBTFUL/UNLIKEI	RECOVERING/ RESOLVING RECOVERED /	Y	N	N	N	N	N
xxx	yyyy-mm-ddThh:mm / yyyy-mm-ddThh:mm	x	CONTINUOUS/ MODERATE	DOSE NOT CHANGED	DEFINITE	RESOLVED WITH SEQUELAE RECOVERED /	Y	Y	Y	Y	Y	N
xxxx	yyyy-mm-ddThh:mm / yyyy-mm-ddThh:mm	x	CONTINUOUS/ MODERATE	DOSE NOT CHANGED	DEFINITE	RESOLVED WITH SEQUELAE	Y	N	N	N	N	N
...						

* Study start date =< Onset date of event: Onset date of event - Study start date + 1, Study start date > Onset date of event: Onset date of event - Study start date

* (a)Did the subject withdraw from the study as a result of this event? / (b)Did the subject experience increased dyspnea? / (c)Did the subject experience increased cough? / (d)Did the subject expectorate sputum?/ more than usual?/ The color / (e)Did the subject increase their usual treatment? / (f)Did the subject take antibiotics or oral steroids?

>Sort order;
 Subject Number, Start Date of Events , Start Time of Events

GTI 1401
 11 Safety Analysis

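### A non-serious COPD exacerbation rated as related to Alpha-1 MP is left out of every ADR count, and the Protocol's own definitions conflict on this

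*SAP*

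**What the plan says.** Two sets of rules bear on the same event.

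**What counts as an ADR.** Protocol 5.3.2 is broad and mentions no COPD exception: "All noxious and unintended responses to a medicinal product or study treatment related to any dose should be considered suspected ADRs". Protocol 5.3.3 gives the working rule, which starts from an event that is already an AE ("When an AE is classified, assessing causal relationship by the Investigator"). Any rating from Doubtful/Unlikely up to Definite makes that AE a suspected ADR; only Unrelated does not.

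**What is kept out of the AE set.** Protocol 4.6.1 says that "COPD exacerbations will not be reported as AEs unless a COPD exacerbation meets the criteria of an SAE", and Protocol 5.3.9 repeats it. The reason given is that exacerbations belong to the expected course of the deficiency. SAP 11.1 carries the rule into its definition of an AE: "In this protocol, non-serious COPD exacerbation will not be considered as adverse events unless SAE". It then adds: "All tables regarding to Adverse Events are restricted to TEAE".

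**What is still collected.** The SAP layout plan has a separate Listing 11.1.11 for non-serious exacerbations, with columns for causality, action taken with study drug, and a yes/no item: "a)Did the subject withdraw from the study as a result of this event".

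Protocol 4.6 names ADRs and discontinuations due to AEs among the study variables. Safety is the primary objective (Protocol 3.1).

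**The concern.** The stated reason for the exclusion is that exacerbations happen anyway in this disease. That is a fair reason for not calling a background exacerbation an adverse event. It does not cover an exacerbation that the investigator has attributed to the infusion, yet neither document separates the two cases.

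The listing shows that relatedness is meant to be recorded for these events, and the plan then gives that information no route into any ADR count. SAP 5.2 makes the contrast sharper: an AE whose relationship is missing is counted as related, as a worst case, whereas a non-serious exacerbation actually rated Definite is not counted at all.

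In a study this small, the ADR table may show no reactions while a related event stands only in a listing that the table does not mention.

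**Working it through.** The documents give no figure for this point, so there is nothing to reproduce. The check is a trace of one hypothetical event through the planned outputs, followed by its size.

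**Step 1. Trace.** Take a non-serious exacerbation after the first infusion, with causality other than Unrelated. Numbers are those of the layout plan.

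| Output | Input | Is the event counted? |
|---|---|---|
| Overview 11.1.1, ADR rows | Treatment-emergent AEs not rated Unrelated | No |
| Tables 11.1.3 and 11.1.6, ADRs and ADRs by severity | Same | No |
| Table 11.1.4, AEs by causality | Treatment-emergent AEs | No |
| Overview 11.1.1, row for "AEs leading to premature discontinuation from the study", and its listing | AEs only | No, even if the subject withdrew because of it |
| Overview 11.1.1, special-interest rows | All exacerbations under the SAP 11.1 definition | Yes by definition, but see Step 2 |
| Table 6.2, discontinuations by reason | Every discontinuation in the Safety population | Yes, if the subject withdrew |
| Listing 11.1.11 | Non-serious exacerbations | Yes, with causality and withdrawal |

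**Step 2. Loose ends in the rows that do include it.**
- The special-interest rows sit in an AE table, and AE tables are restricted to treatment-emergent AEs. A programmer could therefore limit these rows to serious exacerbations. In either case they have no split by causality.
- The list of listings in SAP 11.1 describes the exacerbation listing as one of AEs, which contradicts the definition that precedes it.
- In the Table 6.2 layout, the reasons shown are an adverse event category and a subject-withdrawal category that excludes AEs, with further rows left open. The category for a withdrawal caused by a non-serious exacerbation is not settled.

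**Step 3. Size.** Inputs: a minimum of 3 subjects (Protocol 8.2, SAP 5.4); one related non-serious exacerbation in a subject with no other ADR (my assumption). The shift in ADR incidence is 1/N − 0/N = 1/N.

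| N | Planned ADR incidence | With the event counted | Shift (points) |
|---|---|---|---|
| 3 | 0/3 = 0.0% | 1/3 = 33.3% | 33.3 |
| 4 | 0.0% | 25.0% | 25.0 |
| 5 | 0.0% | 20.0% | 20.0 |
| 6 | 0.0% | 16.7% | 16.7 |

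N = 4 to 6 are assumed, since the documents give only a minimum. The AE-withdrawal row shifts by the same amount if the event caused withdrawal and the subject is not already in that row.

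For scale, the exact (Clopper-Pearson) 95% interval at N = 3 is 0 to 70.8% for 0/3 and 0.8 to 90.6% for 1/3. The intervals overlap heavily. What changes is the reported finding, from no ADR to one subject in three.

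**Step 4. How often it could arise.** The documents give no probability. If each subject independently has probability p of at least one such event, the chance of seeing it in 3 subjects is 1 − (1 − p)³. This gives 0.143 at p = 0.05, 0.271 at 0.10, 0.488 at 0.20 and 0.657 at 0.30. These values of p are assumptions.

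**The case against.** The strongest reply is that there is no conflict. The second sentence of Protocol 5.3.2 explains a response as a causal link between the product and an AE, and 5.3.3 also starts from an AE. ADRs are then a subset of AEs, and a specific, reasoned exclusion narrows a general definition. This reading is available. It removes the formal contradiction but not the effect: a related event still goes uncounted for a reason that does not apply to it.

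The reply also answers several stronger readings that a reader might infer:
- *That the SAP departs from the Protocol.* It does not. It follows Protocol 4.6.1 and 5.3.9, so the tension lies inside the Protocol and is carried over.
- *That withdrawal because of an exacerbation makes it an ADR.* Protocol 5.3.2 and 5.3.3 turn on causality alone. Withdrawal affects only the AE-withdrawal row and listing.
- *That such withdrawals or events disappear.* Table 6.2 counts every discontinuation, Listing 11.1.11 shows each event, and all exacerbations are defined as events of special interest. With about three subjects, each case can be read individually.
- *That infusion reactions will commonly be labelled exacerbations.* Nothing in the documents supports this. The reactions that Protocol 1.3 names for Alpha-1 MP at this dose are chills, malaise, headache, rash, hot flush and itching; none is respiratory.
- *That the mock-up entries foresee a related event.* They are placeholders, and similar ones appear in the general AE listing. Only the existence of the columns is informative.

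One further point stands. Doubtful/Unlikely counts as related, so moving all such exacerbations into the main ADR rate could bring in events that the exclusion reasonably keeps out. That argues for added rows rather than a new AE definition.

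**Conclusion.** The point holds as a gap in the ADR counts. Neither document makes an exception for a non-serious exacerbation rated as related. Such an event is absent from the ADR rows and tables and from the causality table and, if it led to withdrawal, from the row and listing of AEs leading to discontinuation.

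At the minimum of 3 subjects, one such event in a subject with no other ADR changes the reported incidence from 1/3 to 0/3. The direction is fixed: the rule can lower the ADR count but never raise it. The size rests on two assumptions, that such an event occurs and that the subject has no other ADR; the documents say nothing about how likely either is.

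The documents do not support a claim that the data are lost, that all discontinuation counts are affected, or that the SAP contradicts the Protocol. This is a low-cost improvement to the safety tables.

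**What to change.** In SAP 11.1.1 and the matching layout:
1. State that the special-interest rows include non-serious exacerbations, despite the restriction of AE tables to treatment-emergent AEs.
2. Add rows, for subjects and for events, giving non-serious exacerbations not rated Unrelated, split by causality category (Definite, Probable, Possible, Doubtful/Unlikely).
3. Add rows for non-serious exacerbations with item (a) of Listing 11.1.11 answered Yes.
4. Present an ADR count that includes the related exacerbations beside the planned ADR count, which stays as it is.
5. Footnote the ADR tables to Listing 11.1.11.

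In the Protocol, reconcile 5.3.2 with 4.6.1 and 5.3.9, so that the status of a related non-serious exacerbation is stated once.

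The cost is a few table rows, SAP wording, a programming condition on fields that Listing 11.1.11 already displays, and a Protocol clarification. Listing 11.1.11 shows no MedDRA columns, so these events may need coding if they are to be shown by system organ class and preferred term. The supplementary ADR rate may look less favourable and may include exacerbations rated only Doubtful/Unlikely; the split by causality makes that visible.

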4.2. Selection of Subject Population

Eligible subjects must provide written consent to participate in this clinical trial of their own free will after being fully informed of the contents of the trial based on the written information and informed consent form.

After obtaining written informed consent from each subject, the investigator or subinvestigator will screen the subject within 21 days before the first investigational drug infusion. The investigator will assess subject eligibility based on the inclusion criteria and the exclusion criteria below.

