For any subject, all AEs that occur at any time from the beginning of Alpha-1 MP administration until the final visit of the clinical trial will be considered as TEAEs.

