5.3.7 Recording of Adverse Events

All AEs and SAEs occurring after the subject has signed the ICF through the End of Study must be fully recorded in the subject's CRF and SAE form if applicable. If no AE has occurred during the study period, this should also be indicated in the CRF.

It is responsibility of the Investigator to ensure that AEs are appropriately recorded.

At each visit, AEs will be elicited by asking the individual a non-leading question such as "Do you feel different in any way since the last visit?". Moreover, AEs will also be collected through directly observed events or spontaneously volunteered by the subject. Clearly related signs, symptoms and abnormal diagnostic procedures should preferably be grouped together and recorded as a single diagnosis or syndrome wherever possible.

The following variables must be recorded on the AE CRF entry:

1. The verbatim term (a diagnosis is preferred)
2. Date/time of onset
3. Date/time of resolution
4. Severity (mild, moderate, severe)
5. Causality (unrelated, doubtful/unlikely, possible, probable, definite)*
6. Seriousness (yes, no)
7. Action taken (with regard to investigational product)
8. Other action (to treat the event)
9. Outcome and sequel (follow-up on AE)

**Causality assessment will be only made when the AE occurs after the subject has initiated at least one infusion of the investigational product. Any AE occurring before subject's exposure to investigational product will be always labeled as "unrelated".*

In addition to the Investigator's own description of the AEs, each AE will be encoded by the Sponsor (or Contract Research Organization [CRO]) according to the Medical Dictionary for Regulatory Activities (MedDRA®).

For example, a laboratory test abnormality considered clinically relevant, e.g., causing the subject to withdraw from the study, requiring treatment or causing apparent clinical manifestations, or judged relevant by the Investigator, should be reported as an AE. Each

event must be described in detail along with start and stop dates, severity, relationship to investigational product, action taken and outcome. Each event must be adequately supported by documentation as it appears in the subject's medical or case file.

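### The GTI1401 TEAE rule has no worsening clause, so a screening AE with a complete onset date that worsens after dosing and stays on one record is missing from the GTI1401 AE and ADR tables.

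*SAP*

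**What the plan says.** SAP 11.1 defines a GTI1401 TEAE as "any adverse event occurred after or on the first study drug infusion of GTI 1401 to the final visit of GTI 1401". Protocol 5.3.3 treats as TEAEs "all AEs that occur at any time from the beginning of Alpha-1 MP administration until the final visit of the clinical trial". Neither definition mentions an event that is already present at the first dose and then gets worse. The SAP adds: "All tables regarding to Adverse Events are restricted to TEAE".

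Collection starts before dosing. Under Protocol 5.3.7, "All AEs and SAEs occurring after the subject has signed the ICF through the End of Study must be fully recorded", and under Protocol 4.2 the investigator "will screen the subject within 21 days before the first investigational drug infusion". Screening-onset AEs can therefore be in the database.

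On causality, the footnote in Protocol 5.3.7 says: "Causality assessment will be only made when the AE occurs after the subject has initiated at least one infusion of the investigational product". It adds that an AE before the subject's "exposure to investigational product will be always labeled as" unrelated. Protocol 5.3.3 and SAP 11.1 both count an AE as a suspected ADR only if its causality category is something other than unrelated.

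**The concern.** Safety is the primary objective (Protocol 3.1, SAP 3.1) and the analysis is descriptive, so the AE and ADR tables are in effect the primary result. A pre-existing complaint that worsens after an infusion is something those tables ought to show. Under the written rules it can drop out twice: once because its onset is before the first dose, and again because its causality was fixed before exposure. The AE overview (SAP 11.1.1) also counts SAEs, fatal AEs and AEs leading to discontinuation. A screening AE that turned serious or led to withdrawal after dosing could be missing from those rows too.

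**Working it through.** The plan states no figure to reproduce. The check is to follow one hypothetical event through the rules: mild, complete onset date in screening, severe after an infusion, kept on a single record.

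1. **Is it in the data?** Yes. AEs are recorded from consent, up to 21 days before the first infusion (Protocol 5.3.7 and 4.2).
2. **What does the record hold?** The AE entry listed in Protocol 5.3.7 has one onset, one resolution and one severity. The AE listing shell (SAP layout plan 11.1.7) has one start/end pair beside a pattern field, intermittent or continuous. No text in either document asks for a second record when an event worsens.
3. **Which date sets the TEAE flag?** The start date. The SAP 11.1 rule beginning "Adverse events with incomplete start dates will be considered treatment emergent (TEAE) if" compares the AE start date with the first dose date. With a complete pre-dose date, the event is not a TEAE.
4. **Does the worst-rating rule rescue it?** No. SAP 11.1 gives precedence to the most severe rating or strongest relationship when the same event appears more than once. That selects the rating to tabulate. It does not change the TEAE flag.
5. **Can it be an ADR?** No. The label *unrelated* is assigned, so the SAP 5.2 rule that treats a missing relationship as related does not apply.
6. **Where does it appear?** In the listings only, which carry a TEAE column (layout plan 11.1.7 and 11.1.9).
7. **What about the extension?** The GTI1401-OLE definition in SAP 11.1 also counts AEs continuing from GTI1401. An event still ongoing at extension entry therefore enters the OLE AE tables, although its *unrelated* label would keep it out of the OLE ADR counts unless causality were reassessed. The GTI1401 definition has no matching carry-over or worsening provision.

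**Scale.** The stated minimum is 3 subjects (Protocol 8.2, SAP 5.4). Suppose one subject is affected and has no other TEAE, and the other two have none:
- as written: 0/3 = 0%
- with the worsening counted: 1/3 = 33.3%
- difference: 33.3 percentage points in the *at least one AE* row

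If that subject has another TEAE, this row does not move. A preferred-term or severity row still moves by 1/3 if the subject has no other qualifying event in it.

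**The case against.** Both definitions speak of events that occur, not events that start. A clinically meaningful worsening after an infusion could itself meet the AE definition and be entered as a new event with a post-dose onset. The rule for the same event at more than one severity is compatible with that practice. Protocol 9.1 also refers to a separate CRF completion procedure, which is not among these documents and may settle the matter. The *unrelated* label is worded for AEs occurring before exposure, and Protocol 5.3.3 says an AE whose relationship cannot be ruled out may not be called unrelated.

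The signal also has other routes. Laboratory, vital-sign, ECG and lung-function summaries (SAP 11.2, 11.3, 11.4 and 11.6) are not limited to TEAEs. SAEs are reportable within 24 hours from consent onward (Protocol 5.4.1). With so few subjects, the listings will be read line by line.

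Much of this stands. It makes the exclusion conditional on the event staying on one record, and it means the event is not hidden altogether. It does not close the gap. Neither document instructs sites to open a new record, and the flag rule works from the start date. A listing entry marked not treatment-emergent and unrelated does not supply the missing causality assessment.

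Three stronger readings are tempting but not supported:
- **That such events vanish from every AE table in the SAP.** They do not. The OLE tables take in continuing events, and the incomplete-date rule counts some screening AEs as TEAEs, for example one with the day missing in the month of first dose.
- **That the share of collection time spent in screening measures the risk.** That share is at most 21/(21 + 56) = 27% for subjects who finish at Week 9, or 21/(21 + 77) = 21% for those followed to Week 12. It is not the probability that an AE starts in screening, persists to dosing and then worsens.
- **That the change would affect non-serious COPD exacerbations.** These are kept out of AEs by a separate rule (Protocol 4.6.1 and 5.3.9) and have their own listing.

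**Conclusion.** The concern holds for GTI1401 in a limited form. The TEAE rule turns on onset relative to the first infusion, has no worsening clause, and is not backed by any recording instruction. The result is a possible undercount in the primary safety tables under the rules as written. Protocol and SAP agree with each other here, so both need the change.

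The conclusion rests on three conditions: the event has a complete screening onset date, it worsens after dosing, and it stays on one record. How often that would happen cannot be estimated from the documents. The 33-point shift applies at exactly 3 treated subjects, with one affected subject who has no other TEAE. The plan states only a minimum number of subjects, and the shift shrinks as more are enrolled. This should be corrected, but it does not invalidate the plan.

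**What to change.** - **SAP 11.1 and Protocol 5.3.3:** extend the GTI1401 TEAE definition with *or an AE with earlier onset that worsens in severity, seriousness or frequency on or after the first infusion*.
- **Protocol 5.3.7:** have sites record the worsening as a new AE with its own onset date and causality assessment.
- **Protocol 5.3.7 footnote:** state that the automatic *unrelated* label applies only to the pre-dose record.

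The definition and the recording instruction are needed together. A single record with one severity does not show that an event worsened, so the new definition could not be applied from it.

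The cost is wording in the protocol, the SAP and the CRF guidance. The TEAE count, and possibly the ADR count, may be slightly less favourable.
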